Via treating neurologists (MS clinic or community-based) and/or nurse practitioners; flyers sent through social media newsletters MS Canada and MS research portal via MS Canada and in clinic rooms/waiting rooms neurologists' practices; mass secure patient messaging via connectcare electronic medical records system

Randomization:

n/a

Intervention:

Eligible patients will download the My Normative app, by scanning a link/QR code. Once registered, electronic consent will be collected through the app. Participants will fill out a baseline series of demographics in addition to a series of patient-reported outcome measures (fatigue, patient perceived level of disability, MS patient symptoms screen, sleep, self-efficacy scale, self-perceived cognition and coping levels, motivation for cognition, and depression and anxiety levels) on the app, as well as enter information re: menstrual cycle tracking/hormone levels as prompted by the app. Participants will then track their menstrual cycles for 6 months with completion of patient reported outcome measures: (1) fatigue – MFIS – 5 item;²⁻⁴ (2) depression & anxiety - HADS;⁵ (3) coping (mini-COPC); (4) MFC – motivation for cognition;⁶ (5) MSymptoscreen (screen of common MS symptoms)⁷ and likert scale from 0 to 7 as to self-perceived cognition levels. This will be done five times per month, as per the different phases of the menstrual cycle. At the end of 6 months, participants will complete an exit scale – with all of the above.

Duration of Study Involvement:

6 months (this has been determined to be optimal in capturing 3 months of menstrual cycles)

This study will be a 2 year study with rolling enrollment

Primary outcomes:

Difference in modified MFIS (fatigue) levels, 5 items during menstruation compared to other times of the menstrual cycle ^{3, 4, 8-10}.

Secondary outcomes:

Qualitative self-reported difference:

- **HADS** (Hospital anxiety and depression scale) – 14 items ⁵
- **MNSQ** (Multiple Sclerosis Neuropsychological Screening Questionnaire–Patient Version) - 15 items ¹⁰⁻¹³
- **Two Likert scale** – self perceived cognition levels (0 to 7)
- **Coping** – MS specific – Brief COPE Short Version (Mini-Cope) – 12 items (3 different coping styles: active/adaptive, avoidant/maladaptive, and emotional/neutral ¹⁴)
- **MFC scale** (motivation for cognition)⁶

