A recent prospective study examining MS symptom severity variability at points throughout women's menstrual cycle was published in 2023; participants reported a number of symptoms at different points during their menstrual cycles and there was a suggestion of less fatigue as measured by the MFIS during the perimenstrual period as compared to the luteal period, not felt to be clinically significant, as well as less variability in fatigue reported by women on continuous hormonal oral contraception compared to those who weren't. The authors conclude that more studies are needed to examine the possible relationship between menstruation and MS symptoms.⁴²

The My Normative platform app has been used in other populations to track menstrual cycles in relation to various symptoms for women in the general population and other conditions.(mynormative.ca) We hope to examine MS-related symptoms to stages of the menstrual cycle, as measured by the My Normative platform.(mynormative.ca) We hypothesize that MS-related fatigue would be greater in the luteal phase of the cycle as compared to other times of women's menstrual cycles, as measured by the MFIS-5 item.³ Secondary outcomes will include impact of menstrual cycle stage upon cognition as measured by the likert scale of self-perceived cognitive levels from 1 to 7, various MS symptoms as measured by the SymptoMScreen (walking, hand function/dexterity, spasticity & stiffness, bodily pain, sensory symptoms, bladder control, fatigue, vision, dizziness, cognition function, depression, anxiety),⁷ MFC scale (motivation for cognition)⁶ and coping (the mini-cope)¹⁴ over a 6 month period with a minimum of 3 months of menstrual cycle tracking. The My Normative platform tracks menstrual cycles in five phases: (1) menstrual phase; (2) follicular phase; (3) ovulation phase; (4) Luteal phase early; (5) luteal phase late

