2.0 Proposed Research

Hypothesis:

Women with MS experience worsening of fatigue, as self-reported by MFIS, during menstruation compared to other times during their menstrual cycles.

Design:

Prospective observational self-enrolled study on mobile app.

Setting:

online, app reporting

Subjects:

Females living with MS, who experience menstruation.

Inclusion Criteria:

Participants are required to meet the following criteria:

- Females with diagnosed MS by 2017 McDonald criteria ¹ (biologically sex-based, any gender as long as not on hormonal gender-enhancing therapy)
- ages 16+, still experiencing menstruation with cycles of 23 to 36 days spacing
- have entered menarche, are experiencing menstrual cycles, and have not yet entered menopause
- participants may utilize hormonal contraceptive methods, such as oral contraceptive methods or hormonal IUDs
- English-speaking
- Willing to provide informed consent, mature minors will provide informed consent, their physician will determine whether their level of maturity is appropriate to participate in the study and complete consent as a mature minor
- Have the ability to complete questionnaires and operate the app

Exclusion Criteria:

People will be excluded as per the following criteria:

- diagnosed with other CNS inflammation disorders than MS
- male or intersex individuals, given the inclusion criteria of requiring a uterus
- females < 15 years of age
- females who have not started menstruation
- females who have stopped menstruation due to menopause or hysterectomy

- pregnant or postpartum women x 1 year after delivery and/or people who currently breastfeeding
- are unable to provide informed consent
- are unable to complete questionnaires and operate the app

Randomization:

n/a

Questionnaires:

Baseline:

- **PDDS** – single scale (physical disability measure) Patient Determined Disease Steps ⁴³
- **Full MFIS** – Modified Fatigue Impact Scale (21 point scale) – fatigue ^{2, 8, 9}
- **HADS** (anxiety & depression) – Hospital Anxiety & Depression Scale (14 items)⁵
- **PHQ9** – Patient Health Questionnaire (depression & anxiety) (9 items)^{44, 45}
- **MSNQ** (cognition) (15 item)¹¹⁻¹³
- **Mini Cope** (coping) (12 item)⁴⁶
- **Pittsburgh sleep quality index** (sleep quality) (24 items)⁴⁷
- **the SymptoMScreen** (12 item) (walking, hand function/dexterity, spasticity & stiffness, bodily pain, sensory symptoms, bladder control, fatigue, vision, dizziness, cognition function, depression, anxiety)^{7, 42}

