- **MFC scale** (Motivation for Cognition) (10 item)⁶
- **General factors**
 - Demographics (age, race, ethnicity, marital status, level of education, # children, working outside/inside home), BMI, smoking status
 - Years since onset MS (first symptoms) and diagnosis
 - Disease modifying therapies list
 - Medications listt
- **Menstrual cycle information**
 - Length of cycle
- **Type of contraception**
 - Rhythm method
 - No contraception
 - Barrier
 - Condoms
 - Diaphragm
 - IUD (with hormone, without hormone)

- OCP – type – continuous/not continuous
- **5 time points during the menstrual cycle**
 - 1) Follicular phase, during active menstruation
 - 2) Follicular phase, no menstruation (leading up to ovulation)
 - 3) ovulation phase
 - 4) Luteal phase, first half
 - 5) Luteal phase, second half (this is the 5-7 days before the next period starts)

Each time point:

- MFIS brief 5 item ³
- Cognition Likert scale – self perceived cognition levels (0-7)
- SymptoMSScreen 12 item ⁷
- Mini-COPE (12 item)¹⁴
- MFC scale (motivation for cognition) 10 item⁶
- Longer MFIS point scale once per cycle, alternating timing of long scale done at each time point (3 points within cycle) over study duration (6 months) ^{2, 8, 9}

Study Completion:

- **PDDS** – single scale (physical disability measure) Patient Determined Disease Steps⁴³
- **Full MFIS** – modified fatigue Impact Scale (21 point scale) – fatigue^{2, 8, 9}
- **HADS** (anxiety & depression) – Hospital Anxiety & Depression Scale – 14 items ⁵
- **PHQ9** – patient health questionnaire (depression & anxiety) – 9 items ^{44, 45}
- **MSNQ** (cognition) 15 item ¹¹⁻¹³
- **Cognition Likert scale** – self-perceived cognition levels (0 – 7)
- **Mini Cope** (coping) (12 item) ⁴⁶
- **Pittsburgh sleep quality index** (sleep quality) 24 items ⁴⁷
- **the SymptoMSScreen** - 12 item (walking, hand function/dexterity, spasticity & stiffness, bodily pain, sensory symptoms, bladder control, fatigue, vision, dizziness, cognition function, depression, anxiety) ⁷
- **MFC scale** (motivation for cognition) – 10 item ⁶
- Relapses in past 6 months/use of steroids
- Optional - agreement to be contacted to participate in qualitative interview re: use of app

Sample size:

There is not much information or data to calculate sample size. We plan to recruit 300 women living with MS for this study as a convenience/availability sample from the two

MS Clinics at the University of Alberta and University of Calgary (approximately 150 per site).

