Taylor et al completed a pilot study, published in 2023, on menstrual cycle and fatigue symptoms in eumenorrheic women living with MS. There was a suggestion of less fatigue in the perimenstrual period compared to the luteal portion of the cycle, and less fluctuation in symptom severity over the cycle for women on continuous hormonal oral contraception. There was a lot of difficulty recruiting for this study with over 200 women contacted and 70 enrolled and 47 providing more than 4 weeks of data for a 6 month period.⁴² Despite the challenges faced by these authors, and anticipating a 20% dropout, we plan to try to recruit a maximum of 300 participants over 2 years. There are no substantial prior studies to base the sample size calculation upon.

Analytical Plan:

We will calculate summary statistics for primary and secondary outcomes across different menstrual cycle phases. We will conduct hypothesis tests (e.g., t-tests, ANOVA) to determine if there are statistically significant crude differences in MS symptom severity or relapse rates among different menstrual cycle phases and explore the relationship between the timing of the menstrual cycle and MS symptom severity using correlation coefficients (e.g., Pearson's correlation). We will perform regression analysis to identify any potential predictors of MS symptom severity, including menstrual cycle phase, age, duration of MS, and other relevant covariates and stratify the analysis by age groups to explore for effect modification by reproductive stage of youth, early adulthood (reproductive years) and later adulthood (peri-menopause), respectively defined as participants < 20 years old, 20 to 40 years old, > 40 years old. We will control for potential confounding variables, such as medication use, comorbidities, and lifestyle factors, in these adjusted models. Finally, we will perform sensitivity analysis to assess the robustness of the results by varying assumptions or analytical methods. Finally, we will provide descriptive measures of baseline characteristics/demographics.

Feasibility:

This study will be carried out through the reciprocal ethics process at the Universities of Alberta and Calgary. Each MS Clinic at each clinic follows about 5000 PwMS in Alberta. MS affects 3 women to every man, with average onset between ages 20 to 40. Therefore, both clinics see many women with MS who are at ages who experience menarche.

Timelines:

2 years, each site to recruit 150 participants maximum

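### The Analytical Plan does not say how about 15 to 40 fatigue records from the same woman will be handled; pooled as independent, they give wrong standard errors for phase and for woman-level predictors

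*Combined protocol and SAP*

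**What the plan says.** **Data collection.** The Intervention section says of the questionnaires: "This will be done five times per month, as per the different phases of the menstrual cycle". Under Questionnaires in section 2.0, the list headed "5 time points during the menstrual cycle" is followed by the scales due at each of them: MFIS-5, cognition Likert, SymptoMScreen, Mini-COPE and MFC. Follow-up is six months. Duration of Study Involvement adds that "this has been determined to be optimal in capturing 3 months of menstrual cycles", and section 1.0 describes collection "over a 6 month period with a minimum of 3 months of menstrual cycle tracking".

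**Primary question.** Primary outcomes gives "Difference in modified MFIS (fatigue) levels, 5 items during menstruation compared to other times of the menstrual cycle". The Hypothesis in section 2.0 agrees: "Women with MS experience worsening of fatigue, as self-reported by MFIS, during menstruation compared to other times during their menstrual cycles". Section 1.0 instead expects that "MS-related fatigue would be greater in the luteal phase of the cycle as compared to other times".

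**Analysis.** The Analytical Plan is one paragraph. It says "We will conduct hypothesis tests (e.g., t-tests, ANOVA) to determine if there are statistically significant crude differences in MS symptom severity or relapse rates" among phases. It then names Pearson correlation, a regression with phase, age, MS duration and other covariates as predictors, three age strata, confounder adjustment and a general sensitivity analysis. No section mentions pairing, repeated measures, a woman effect, clustered standard errors, averaging within woman, or a unit of analysis.

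**The concern.** The primary comparison is made within each woman, but the methods named, in their standard form, treat every record as a separate person. Pooling does opposite things to the two kinds of predictor in the planned regression.

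- Phase changes within a woman. Stable differences between women stay in the error term, so the test is normally too cautious and loses power.
- Age and MS duration are essentially fixed for each woman. Her repeated rows count as new women, so the test rejects far too often.

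There is a third possibility. If women differ in how they respond to phase, the pooled phase test can become too liberal. At stake are missed phase effects and spurious predictors of symptom severity, in a study that hopes to inform when in the cycle symptoms might be addressed.

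**Working it through.** The plan has no calculated figure to reproduce: 300 is a convenience maximum, with no alpha, power, SD or effect size.

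**Inputs from the document**
- Women: 300 less the 20% dropout in Sample size, 300 × 0.8 = 240.
- Records per woman (m): three cycles, 5 × 3 = 15; five per month, 5 × 6 = 30; with eligible cycles of 36 and 23 days, 5 × 182.6/36 = 25 and 5 × 182.6/23 = 40.

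**Assumptions:** two-sided 0.05, total SD 1, ICC 0.3 to 0.7 (0.1 also shown), complete balanced data.

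**1. Phase contrast, common phase effect.** Over c cycles there are 240c menstruation records and 960c others.
- Pooled SE = √(1/(240c) + 1/(960c)) = 0.0295 (c = 6) or 0.0417 (c = 3).
- True SE = pooled SE × √(1 − ICC).
- Effect with 80% within-woman power: d = 2.80 × true SE.
- Pooled power = Φ((d − 1.96 × pooled SE)/true SE).

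| ICC | Pooled/true SE | Pooled power at d | 0.10 SD, c = 6: pooled vs within | 0.10 SD, c = 3: pooled vs within |
|---|---|---|---|---|
| 0.3 | 1.20 | 68% | 96% vs 98% | 70% vs 82% |
| 0.5 | 1.41 | 51% | 98% vs 99.8% | 73% vs 92% |
| 0.7 | 1.83 | 22% | 99.6% vs 100% | 79% vs 99% |

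The effect d is 0.069, 0.058 and 0.045 SD at six cycles, and 0.098, 0.083 and 0.064 SD at three.

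**2. Woman-level predictors.** Design effect DE = 1 + (m − 1) × ICC; type I error = 2 × [1 − Φ(1.96/√DE)].

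| m | ICC 0.1 | ICC 0.3 | ICC 0.5 | ICC 0.7 |
|---|---|---|---|---|
| 5 | 10% | 19% | 26% | 31% |
| 15 | 21% | 39% | 49% | 55% |
| 30 | 32% | 53% | 62% | 67% |
| 40 | 38% | 58% | 67% | 71% |

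For example, m = 15 and ICC 0.3 give DE = 1 + 14 × 0.3 = 5.2 and 39.0%. Simulation with 240 women gave 39.8% (m = 15, ICC 0.3), 61.5% (m = 30, ICC 0.5) and 69.9% (m = 40, ICC 0.7). Using one mean per woman gave 4.0% to 5.9%.

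**3. Phase response varying between women.** Let v be the woman-by-phase variance as a share of the total, and e = 1 − ICC − v.
- True SE = √(1.25 × (v + e/c)/240).
- Pooled type I error = 2 × [1 − Φ(1.96 × pooled SE/true SE)].
- At c = 6, v = 0.2, ICC 0.3: true SE = √(1.25 × 0.2833/240) = 0.0384, so the error is 13.3%.
- At c = 6, v = 0.05, the error is 0.8% to 4.4% over ICC 0.7 to 0.3, still below 5%.
- At c = 3, v = 0.05 to 0.2, it runs from 0.2% to 6.2%.

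**4. Random woman intercept alone.** Its residual variance is about r = (4cv + (5c − 1)e)/(5c − 1), and its SE is √(1.25 × r/(240c)).
- At c = 6, v = 0.05, ICC 0.3: SE 0.0245 against a true 0.0287, error 9.4%.
- At c = 6, v = 0.2, ICC 0.7: SE 0.0152 against a true 0.0336, error 37.6%.
- At v = 0.01, six cycles, the error is about 6% to 7%; at v = 0 the model is correct.

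Simulation at c = 6, v = 0.2 and ICC 0.3/0.5/0.7 gave 23.4/28.0/37.4% for the random intercept alone, 5.1/5.4/5.1% with a woman-by-phase effect added, and 5.2/5.4/5.0% for the paired test.

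**The case against.** The strongest reply is that the tests are offered as examples. A paired t-test, repeated-measures ANOVA or mixed regression would all fit the wording, so the plan is under-specified rather than committed to a wrong method. That is correct. A reader might infer that the sponsor intends to pool; the document does not say so, and every size above is conditional on it.

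The sizes also rest on an assumed ICC. The 71% figure needs ICC 0.7 and every woman on a 23-day cycle with full completion. In the pilot that the protocol cites, only 47 of 70 enrolled women gave more than four weeks of data. With five records each, inflation is 19% to 31% at ICC 0.3 to 0.7. It is smaller, but still well above 5%.

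A reader might also infer that the primary fatigue result carries a 39% to 71% false-positive rate. It does not: that range belongs to the regression on woman-level predictors. For the primary contrast the default effect of pooling is lost power, and with complete data the crude phase difference itself is unbiased. The liberal case needs sizeable woman-by-phase variance, for which the document gives no value.

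Finally, the conflict between the menstruation and luteal hypotheses is a separate inconsistency and adds no weight to the clustering point. It matters here because the model's primary contrast cannot be written until it is settled: the menstruation contrast puts the luteal phases in the comparator.

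**Conclusion.** The gap is real and should be fixed before analysis. Permitting a suitable method does not specify one, and for a within-woman primary outcome this choice drives the standard errors and p-values. If records are pooled:

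- the primary phase test is normally conservative, with a material loss of power at three cycles and a small one for a 0.10 SD effect at 240 women and six cycles;
- tests of age, MS duration and similar predictors are seriously anti-conservative at every ICC and record count examined, though how seriously depends on both;
- the phase test turns liberal only if phase response varies strongly between women.

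Confidence is high in the omission and the direction of these effects, and lower in the sizes. They assume alpha, ICC, variance components and complete data, whereas Methodologic Issues lets women withdraw simply by not responding.

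**What to change.** In the Analytical Plan, for MFIS-5 and every scale repeated by phase:

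1. Replace independent-sample tests with a linear mixed model: phase as a five-level factor, a random woman intercept and a random woman-by-phase effect. This keeps women with incomplete phases. A random intercept alone can be too liberal if phase response varies between women.
2. Use a paired t-test of each woman's menstruation mean against her mean over the other phases as a simple check.
3. Test age, MS duration and other woman-level predictors in that model or on one mean per woman.
4. Reconcile the menstruation hypothesis (Primary outcomes and both Hypothesis sections) with the luteal hypothesis in section 1.0, and state one primary contrast before analysis.
5. Reconcile whether HADS is repeated by phase: the Intervention section lists it, but the list of scales for each time point does not. Apply the same model if it is.
6. Report completion by phase.

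Relapses and scales collected only at baseline and completion are not covered by this change. The cost is analysis wording and a few lines of code, with no extra data.

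### Relapse rates are to be compared between menstrual phases, but the only relapse item described is a six-month look-back at study exit with no onset date or phase

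*Combined protocol and SAP*

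**What the plan says.** The Analytical Plan (section 2.0) names t-tests and ANOVA as examples of the tests to be used for "statistically significant crude differences in MS symptom severity or relapse rates among different menstrual cycle phases". Relapse rate is thus a stated dependent variable, with cycle phase as the comparison factor.

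The Background (section 1.0) states that "The My Normative platform tracks menstrual cycles in five phases", and section 2.0 lists five matching time points. The Intervention paragraph of the opening synopsis says of the repeated questionnaires: "This will be done five times per month, as per the different phases of the menstrual cycle". The list for each time point in section 2.0 starts with "MFIS brief 5 item" and continues with the cognition Likert scale, SymptoMScreen, Mini-COPE, the motivation-for-cognition scale and, once per cycle, the longer MFIS.

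Relapse appears in one collection list only, Study Completion, as "Relapses in past 6 months/use of steroids".

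**The concern.** A comparison of relapse rates between phases needs relapses counted within each phase and time at risk in each phase. App tracking of cycles could supply the time at risk. The relapse count by phase has no described source. An item that looks back over six months takes one value per woman. That value is the same whichever phase is considered, so it cannot differ between phases.

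Two things are at stake. First, a test the plan promises cannot be delivered from the data it describes. Second, the gap cannot be fully repaired later: relapse dates noted close to onset cannot be collected once a woman has finished follow-up. Because the item is asked only at exit, women who withdraw by ceasing to answer the app, which the Methodologic Issues section allows, would give no relapse information at all.

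**Working it through.** The plan states no figure for relapse, so there is none to reproduce. The check is a comparison of the lists, followed by some arithmetic on scale.

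**1. Where relapse is collected**

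| Place in the document | Relapse item? |
|---|---|
| Synopsis, Intervention: measures repeated by phase | No |
| Synopsis, Intervention: "participants will complete an exit scale", made up of those same measures | No |
| Section 2.0, Baseline questionnaires and general factors | No |
| Section 2.0, Each time point | No |
| Section 2.0, Study Completion | Yes, one six-month look-back entry |
| Primary and secondary outcomes | No |

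No part of the document describes a relapse onset date, a definition of relapse, a rule for assigning a relapse to a phase, or a link to clinic records. SymptoMScreen is collected at each phase, but as a symptom-severity measure; no use of it to detect relapses is described.

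**2. How much time the exit item covers**

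Inputs: eligibility requires women "still experiencing menstruation with cycles of 23 to 36 days spacing"; follow-up is 6 months, taken as 182.6 days.

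- Longest cycles: 182.6 / 36 = 5.1 cycles; at five phases each, 25.4 phase windows.
- Shortest cycles: 182.6 / 23 = 7.9 cycles; at five phases each, 39.7 phase windows.

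One exit summary therefore stands for about 25 to 40 phase windows per woman.

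**3. The other half of the same sentence**

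Symptom severity can be compared by phase, because MFIS-5, the Likert scale and SymptoMScreen are collected at every time point. Only the relapse half lacks data.

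**4. What a dated item would add to each prompt**

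- List in section 2.0: 5 (MFIS-5) + 1 (Likert) + 12 (SymptoMScreen) + 12 (Mini-COPE) + 10 (motivation for cognition) = 40 items.
- Synopsis list, which also has HADS (14 items): 40 + 14 = 54 items.
- One extra item is 1/40 = 2.5% or 1/54 = 1.9%. Both counts leave out the once-per-cycle longer MFIS.
- Number of prompts: 5 per month × 6 months = 30. If prompts follow phases rather than calendar months, the count is the 25 to 40 found above.

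**5. How many relapses there might be (illustration only)**

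The documents give no relapse rate. I assume 0.1 to 0.4 relapses per woman per year. The sample is taken at its planned maximum of 300, with the Sample size section "anticipating a 20% dropout".

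- Women: 300 × 0.8 = 240. Person-years: 240 × 0.5 = 120.
- Relapses: 120 × 0.1 = 12, up to 120 × 0.4 = 48.
- Average per phase: 12/5 = 2.4, up to 48/5 = 9.6 (a simple average; phases differ in length).
- Suppose also that menstruation takes 5 of 28 days and that the relapse rate doubles in it. The expected share of relapses in menstruation is then 2(5/28) / [2(5/28) + 23/28] = 10/33 = 0.303, against 5/28 = 0.179 with no effect. An exact two-sided binomial test at 0.05 has power of about 0.28 with 12 relapses and 0.50 with 48.

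**The case against.** The strongest reply is that the Study Completion entry is a label, not the form. The app screen behind it may ask for a date. If it did, a recalled date could be matched to the cycle log and the test would be possible after all. A simple repair would then be to put an onset date in the exit item, leaving the prompts alone. It can also be said that relapse rates are mentioned once in the Analytical Plan, that the correlation and regression steps that follow concern symptom severity, and that wording curable by deleting three words is a small matter.

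Part of this stands. The finding is about what the document describes, and the form could hold more. But if it does, the plan should say so, and a rule for assigning relapses to phases would still be missing. Dates recalled over as much as six months are also a weak basis for phases that last days: section 2.0 puts the late luteal window at 5 to 7 days. The limited reach of the problem is accepted and is reflected in the verdict. The event counts depend on an assumed rate, on enrolment reaching 300, and on counting no follow-up from women who drop out. They show only that events would probably be few, and the conclusion does not rest on them.

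**Conclusion.** The concern holds. The plan promises a comparison of relapse rates between phases, and the data it describes provide no phase-specific relapse count: one summary per woman where five phase values are needed. This follows from the collection lists alone and needs no assumed figure. Its one condition is that the exit form holds no more than its label shows.

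The point should be corrected, but its effect is contained. Relapse is absent from the objective, the hypotheses and the primary and secondary outcomes, and the MFIS-5 phase comparison is untouched.

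**What to change.** Choose one of two changes; either resolves the mismatch.

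1. **Collect the timing.** At the existing app prompts, add one short item asking whether a new relapse has begun since the last entry and, if so, on what date. Define relapse, link the onset date to the phase recorded by the app, and report relapses per phase-day with confidence intervals. A count model with phase-days at risk (for example Poisson) or a case-crossover method suits such data better than a t-test or ANOVA. Label the analysis exploratory and say that few events are likely. The cost is one item on a prompt of 40 to 54 items, at about 30 prompts per woman, and a minor amendment made before or early in enrolment.

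2. **Drop the test.** Delete the three words that add relapse rates to the between-phase tests, keep the exit item, and report relapses as a descriptive six-month total. This needs no new data and is enough if the timing of relapses is not of interest.

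### The planned correlation of cycle timing with symptom severity leaves timing uncoded and ignores repeated responses; a five-level phase model with a participant effect would serve better

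*Combined protocol and SAP*

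**What the plan says.** The Analytical Plan intends to "explore the relationship between the timing of the menstrual cycle and MS symptom severity using correlation coefficients (e.g., Pearson's correlation". It does not define timing, and Pearson is only an example. The same paragraph plans t-tests or ANOVA for crude differences among phases, and then a regression in which phase is one predictor. How phase enters that regression is not stated.

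Section 1.0 lists the phases the app tracks as "1) menstrual phase; (2) follicular phase; (3) ovulation phase; (4) Luteal phase early; (5) luteal phase late". Section 2.0 numbers the time points in the same order, from "Follicular phase, during active menstruation" to "Luteal phase, second half (this is the 5-7 days before the next period starts".

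On frequency, the Intervention section says: "This will be done five times per month, as per the different phases of the menstrual cycle". Follow-up is 6 months.

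Two directional expectations appear. The primary outcome compares fatigue "during menstruation compared to other times of the menstrual cycle", and the hypothesis in section 2.0 expects worsening "during menstruation compared to other times during their menstrual cycles". Section 1.0 instead expects that "MS-related fatigue would be greater in the luteal phase of the cycle".

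**The concern.** A correlation needs a numeric timing variable, and the numbered phases are the nearest candidate in the text. An ordered score puts late luteal and menstruation at opposite ends, whereas in time they adjoin. Pearson's r on that score responds only to a steady rise or fall from phase 1 to phase 5, and a rank correlation has the same limit. A real phase pattern could then yield a small coefficient that is read as no relationship, beside a clear phase difference from the same data.

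Separately, each woman contributes up to 5 × 6 = 30 responses. If rows are pooled, stable differences between women are counted as noise and the within-woman signal is diluted.

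**Working it through.** The plan gives no target correlation, effect size, SD, alpha or power, so there is no figure of its own to reproduce.

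**Inputs from the documents:** five phases in the order above; at most 300 recruits with 20% dropout, so 300 × 0.8 = 240 women.

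**Assumptions:** a rise of 0.3 within-woman SD, the same in every woman; one value per phase in one cycle; independent within-woman errors; two-sided 5%; intraclass correlation (ICC) 0.3, 0.5 or 0.7.

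**1. What a 1-5 score can see.** With centred scores c = (-2, -1, 0, 1, 2) and phase means p, noise-free r = Σcp / √(10 × Σ(p - p̄)²). The square of r is the share of between-phase variance captured.

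| Pattern, phases 1 to 5 | Calculation | r | Share |
|---|---|---|---|
| Menstruation only (1,0,0,0,0) | -2/√(10 × 0.8) | -0.71 | 50% |
| Luteal (0,0,0,1,1) | 3/√(10 × 1.2) | +0.87 | 75% |
| Both stated hypotheses (1,0,0,1,1) | 1/√(10 × 1.2) | +0.29 | 8% |
| Phases 5 and 1 equally (1,0,0,0,1) | 0/√(10 × 1.2) | 0 | 0% |

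The last row is illustrative and is not a protocol hypothesis. Spearman's coefficient gives the same values for these patterns.

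**2. Pearson over pooled rows, menstruation-only rise.** If the participant is modelled, the linear trend has noncentrality √240 × (-2 × 0.3)/√10 = -2.94, which gives 83% power. If rows are pooled, the total SD is 1/√(1 - ICC) in within-woman units. The test statistic then has mean of about -2.94 × √(1 - ICC) and SD of about √(1 - ICC):

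- ICC 0.3: mean -2.46, SD 0.84, so P(t < -1.96) is about 72%
- ICC 0.5: mean -2.08, SD 0.71, about 57%
- ICC 0.7: mean -1.61, SD 0.55, about 26%

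Simulation gives about 72%, 58% and 27%, with an error of about a percentage point.

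**3. Within-woman menstruation-versus-other contrast, same data.** With weights (1, -¼, -¼, -¼, -¼) the noncentrality is √240 × 0.3/√1.25 = 4.16, so power is about 98% to 99% whatever the ICC. At ICC 0.5 the shortfall therefore has two parts: from about 99% to 83% through the linear score, and from 83% to about 58% through ignoring the participant.

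**4. Overall phase test on 4 df.** The noncentrality is 240 × Σ(μ - μ̄)², where μ = 0.3p.

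- Menstruation only: 240 × 0.09 × 0.8 = 17.3, power 93%.
- Both hypotheses: 240 × 0.09 × 1.2 = 25.9, power 99%. The within-woman linear trend has 31% here (noncentrality √240 × 0.3/√10 = 1.47).

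**5. Where the linear score does better.** For a straight drift (0, 0.25, 0.5, 0.75, 1) × 0.3, the trend has 96% power against 85% for the 4-df test with 240 women, and 65% against 44% with 100. For a luteal-only rise with 240 women, both have 99%.

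**The case against.** The strongest reply is that the fault depends on a coding the plan never adopts. The numbers 1 to 5 are list labels, and Pearson is only an example. The closing rationale speaks of symptoms at particular points in the cycle, which suits phase indicators at least as well as an ordered score. The correlation is exploratory, the ANOVA in the same sentence ignores phase order, and sensitivity analyses with other methods are promised. For each stated hypothesis taken alone, a within-woman linear score does tolerably with 240 women: 83% power for menstruation only and 99% for luteal.

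Most of this stands, and it limits the point. Three stronger readings are tempting but unsupported:

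- A reader might infer that the plan has chosen an ordered score. It has not; the coding is simply unstated.
- A reader might infer that the main phase comparison fails for the same reason. It does not, because ANOVA among phases is unaffected by order.
- A reader might infer that the coefficient is bound to miss the effect sought. Complete loss needs a pattern symmetric about mid-cycle, which the protocol does not hypothesise. For such a pattern, 5% rejection at every sample size is a property of a within-woman trend. Pooled Pearson rejects even less often, below 2% at the ICCs used here.

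What the reply does not answer is that no method is said to handle repeated responses, that phase coding in the adjusted regression is equally open, and that a better analysis needs no new data.

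**Conclusion.** The point holds as a modest one. Timing is uncoded, and no planned method is said to account for the participant. On a 1-5 score the coefficient captures 50% of the between-phase variance for the menstruation hypothesis, 75% for the luteal one and 8% if both are true. Over pooled rows, a menstruation-only rise that a within-woman contrast would find about 98% to 99% of the time is found in about 72%, 58% or 27% of runs.

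The r values depend only on the pattern and on equal weight per phase. The rejection rates rest on the assumed 0.3 SD rise, the ICCs, one cycle and 240 women, none of which except the 240 can be drawn from the documents. The harm from coding is limited to an exploratory result. The silence on repeated responses covers every listed method, but the plan does not exclude a repeated-measures form of them, so it is an omission and not a demonstrated error in the main tests.

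**What to change.** Replace the correlation clause in the Analytical Plan with wording such as:

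> Symptom severity will be analysed by regression with menstrual cycle phase as a five-level categorical factor and participant as a random effect. We will report the overall 4-df phase test, the menstruation-versus-other contrast and the luteal-versus-other contrast, each contrast with a 95% confidence interval. The adjusted regression will use the same phase coding.

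The menstruation contrast serves the primary outcome and the luteal contrast serves the hypothesis in section 1.0. Keeping a correlation with timing coded as menstruation yes/no is not a good substitute: for a luteal rise its noise-free r is -0.41, and the matching contrast has 54% power against 99% for the linear score with 240 women.

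The cost is a few sentences and no new data, since responses are already collected by phase. There are two downsides. The 4-df test loses power to a 1-df trend if the truth is a linear drift (85% against 96% with 240 women, 44% against 65% with 100, at the assumed 0.3 SD). There is also one additional contrast to report.
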